7.1. Study Subjects

7.1.1. Disposition of Subjects

A STROBE flow diagram will be used to describe the disposition of study subjects for analysis of the primary objective. [Figure 1](#) shows an example of a blank STROBE flow diagram.

Allocation:

Since the IMAGE-HBP study is not a randomized study, all study subjects that are enrolled are allocated to the intervention (i.e. receive a pacing lead at the bundle of His for His bundle pacing).

[figure not shown]
Follow-up:

Study discontinuation might include the following reasons:

- Investigator withdrew subject
- Lost to follow-up
- Subject chose to exit
- Subject death
- Subject did not meet eligibility criteria
- Subject does not have an implant of a SelectSecure™ MRI SureScan™ 3830 lead for His bundle pacing

Analysis:

Analysis can only be completed for subjects that have case report forms saved complete. If there is missing data that prevents the analysis of a pre-specified objective then those subjects will be excluded from that objective. There will be no imputation for missing data.

Figure 1 – STROBE Flow Diagram for the IMAGE-HBP Study

7.1.2. CIP Deviations

Deviations from the CIP will be collected on the Study Deviation CRF. Deviations will be summarized in the final report in a table by coded category. Deviation coding will be performed by Medtronic. The number of deviations per category, and the number and percentage of subjects with a deviation in each category will be reported.

7.1.3. Analysis Sets

There will be two analysis sets used in this study:

Analysis Set #1:

This analysis set will be used for the primary objective (implant success), secondary objective #5 (adverse events), and ancillary objectives #1 and #2. Study subjects will be included in this analysis set if an implant is attempted.

A STROBE flow diagram per section 7.1.1 will outline the specific exclusions.

Analysis Set #2:

This analysis set will be used for secondary objectives #1-#4 and ancillary objective #3. Study subjects will be included in this analysis set if they have a successful implant.

7.2. General Methodology

7.2.1. Primary Objective

The primary objective is to assess the implant success proportion of the Medtronic SelectSecure™ MRI SureScan™ Model 3830 pacing lead at the bundle of His for His Bundle Pacing.

The observed implant success proportion will be calculated as follows:

$$\text{Implant Success Proportion} = \frac{\text{\# Subjects with implant success}}{\text{\# Subjects with implant attempt}}$$

A 95% confidence interval for the implant success proportion will be constructed using the Wilson method.

7.2.2. Secondary Objective #1

This secondary objective is to estimate the correlation between the lead position and selective vs. non-selective HBP occurrence at implant.

The relationship between lead position (anterior septum, mid septum, posterior septum) and HBP selectivity (selective vs. non-selective) will be assessed using a logistic regression. Additionally, HV intervals will be compared between the three groups of lead positions using linear regression.

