#### 13.1.3. Sample Size Determination

A sample size of 62 subjects with an implant attempt will produce a two-sided 95% confidence interval with a width equal to 0.15 (using the Wilson method) for the implant success proportion when the observed implant success proportion is 0.9. **Table 8** below shows various scenarios for the precision of the implant success proportion estimate depending on the actual observed data.

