#### 13.2.1.3. Analysis Methods

The relationship between lead position (anterior septum, mid septum, posterior septum) and HBP selectivity (selective vs. non-selective) will be assessed using a logistic regression. Additionally, HV intervals will be compared between the three groups of lead positions using linear regression.

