- Subjects with exclusion criteria required by local law (e.g. age or other)
- Subject with a medical condition that precludes the patient from participation in the opinion of the investigator
- Subject is enrolled in a concurrent study that may confound the results of this study. Co-enrollment in any concurrent clinical study (including registries) requires approval of the study manager or designee.

Subjects who meet all the inclusion and none of exclusion criteria are eligible to be enrolled in the study.

6. Determination of Sample Size

The goal of the study is to assess the implant success proportion of the Medtronic SelectSecure™ MRI SureScan™ Model 3830 pacing lead at the bundle of His for His bundle pacing. A sample size of 50 subjects with an implant attempt will produce a two-sided 95% confidence interval with a width equal to 0.17 (using the Wilson method) for the implant success proportion when the observed implant success proportion is 0.9. The sample size is not driven by a power calculation or any pre-specified threshold for success. [Table 1](#) below shows various scenarios for the precision of the implant success proportion estimate depending on the actual observed data.

Table 1. Estimation Precision for Implant Success Proportion

Observed implant success proportion (N=50 subjects attempting implant)	Width of the two-sided 95% confidence interval
0.96	0.124
0.92	0.157
0.90	0.17
0.86	0.192
0.80	0.218

7. Statistical Methods

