7.4. Handling of Missing Data and Dropouts

If data is missing then there will be no imputation of the data. Instead, subjects with missing data will be excluded.

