7.9.2. Secondary Objective #1

This secondary objective is to estimate the correlation between the lead position and selective vs. non-selective HBP occurrence at implant.

Analysis Dataset:

Analysis set #2 per section 7.1.3.

Analysis Method:

The relationship between lead position (anterior septum, mid septum, posterior septum) and HBP selectivity (selective vs. non-selective) will be assessed using a logistic regression. Additionally, HV intervals will be compared between the three groups of lead positions using linear regression. The logistic regression will be performed in SAS using code similar to:

```
proc genmod data=analysisset2;
  class leadloc;
  model nsHBP = leadloc / dist = bin link=logit;
```

```
run;
```

and the linear regression will be performed in SAS with code similar to:

```
proc glm data=analysisset2;
  class leadloc;
  model HVint = leadloc;
run;
```

Endpoint Definition:

The lead position is identified as anterior septum, mid septum or posterior septum. Location is determined by the implanting physician during implant and verified by Medtronic through evaluation of cardiac CT scan images. The location determined from CT scan will be used in the analysis.

The HBP at implant is classified as either selective or non-selective by the implanting physician based on the definitions specified in section 4.1, Table 1 of the study CIP.

Additional Analysis:

None

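### Secondary Objective #1: the logistic code shown prints only Wald results, which are unusable for any septal position whose leads are all selective or all non-selective; a penalised estimate and an exact test should be pre-specified

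*SAP*

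**What the plan says.** Protocol 13.2.1.3 says that the relation of lead position to selectivity "will be assessed using a logistic regression". SAP 7.2.2 repeats this: "The relationship between lead position (anterior septum, mid septum, posterior septum) and HBP selectivity (selective vs. non-selective) will be assessed using a logistic regression". SAP 7.9.2 gives illustrative code with lead position as a three-level class variable and the statement "model nsHBP = leadloc / dist = bin link=logit". The code requests no TYPE3 (likelihood-ratio) test, exact test or penalised fit. The additional-analysis entry for this objective is empty, and neither document has a rule for a sparse or one-class position.

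The objective uses Analysis Set #2: "Study subjects will be included in this analysis set if they have a successful implant" (SAP 7.1.3). Position is taken from the CT scan. A lead without a usable CT location drops out under SAP 7.4: "Instead, subjects with missing data will be excluded".

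Neither document states an expected split of leads across the three positions, an expected selective share, or a precision target for this objective.

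**The concern.** Every lead has a selectivity class, so rare events are not the issue. The issue is a position with few leads, or with a very high or very low selective share, in which all leads fall in one class. The maximum-likelihood log odds for that position then has no finite value. The program stops at an arbitrary large number with an enormous standard error, and the Wald ratio of the two is close to zero.

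The stated aim of the objective is to estimate an association. In such a table the planned output gives neither an odds ratio nor an interval for the position concerned, and its p-value is uninformative. For fixed position sizes, the chance of this rises as the selective share in any position approaches 0 or 1. A fallback chosen after seeing the table would be post hoc.

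**Working it through.** **1. Number of leads.** SAP section 6: "A sample size of 50 subjects with an implant attempt will produce a two-sided 95% confidence interval with a width equal to 0.17", "when the observed implant success proportion is 0.9". Protocol 13.1.3: "A sample size of 62 subjects with an implant attempt will produce a two-sided 95% confidence interval with a width equal to 0.15" at the same proportion. The Wilson width is 2z·√(p(1−p)/n + z²/4n²)/(1 + z²/n).
- 45/50 gives 0.1701 (stated 0.17).
- 56/62 gives 0.1504 (stated 0.15).

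Both stated figures reproduce. Successful implants are therefore 0.9 × 50 = 45 under the SAP and 0.9 × 62 = 55.8, about 56, under the protocol, before CT losses.

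**2. Worked table (assumed counts).** Selective leads: 15/30 anterior, 4/15 mid, 0/8 posterior, so 53 leads and 19 selective. Modelling non-selective instead only reverses signs.

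*Wald, posterior against anterior.* The result depends on the stopping rule:
- log-likelihood tolerance 1e-4: log OR −12.2, SE 158, p = 0.94;
- tolerance 1e-8: log OR −21.2, SE about 14,200, p = 0.999.

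The mid-against-anterior contrast is unharmed (log OR −1.01, SE 0.69, p = 0.14). With posterior as the reference level, both contrasts have p = 0.94 (tolerance 1e-4) or 0.999 (tolerance 1e-8). GENMOD by default takes the last level as reference. That is posterior if the levels sort by name, which is an assumption about coding.

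*Likelihood ratio from the same fit.*
- Full model: 30 ln 0.5 + 4 ln(4/15) + 11 ln(11/15) + 0 = −29.49.
- Null model: 19 ln(19/53) + 34 ln(34/53) = −34.58.
- Statistic: 2 × (34.585 − 29.493) = 10.18 on 2 df, p = 0.006.

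*Exact.* The Fisher-Freeman-Halton p is 0.0205.

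*Firth.* For this saturated model the penalty equals adding 0.5 to each cell. OR = (0.5/8.5)/(15.5/15.5) = 0.059, 95% profile limits 0.0004 to 0.55, p = 0.008.

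*Proportions with Wilson limits.* 0.50 (0.33 to 0.67), 0.27 (0.11 to 0.52), 0 (0 to 0.32).

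**3. Other tables.** For one-class positions of 3 to 15 leads, with 45 or 55 leads in all, every contrast with that position had Wald p of about 0.999, and the joint 2-df Wald p was 0.92 to 1.00. Three examples of non-selective counts:

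| Counts | Likelihood-ratio p | Exact p |
|---|---|---|
| 6/15, 6/15, 15/15 | 0.00004 | 0.00025 |
| 6/15, 10/25, 5/5 | 0.015 | 0.056 |
| 8/20, 9/22, 3/3 | 0.077 | 0.166 |

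With few leads in the one-class position, the likelihood-ratio p is clearly smaller than the exact p.

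**4. How often (assumed inputs).** For fixed position sizes, the chance of at least one one-class position is 1 − ∏[1 − pⁿ − (1−p)ⁿ].
- Sizes 15/15/15, non-selective rates 0.3/0.4/0.9: 0.9¹⁵ = 0.206 dominates, total 21%.
- Sizes 20/20/4, same rates: 0.9⁴ = 0.656 dominates, total 66%.
- Sizes 20/20/4, rate 0.4 everywhere (no position effect): 0.6⁴ + 0.4⁴ = 0.155, total 16%.

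The last line shows that a very small position can be one-class by chance. The more relevant count is therefore a one-class position in a table whose exact p is also below 0.05. With random position sizes, 45 to 55 leads and selective shares 0.5/0.3/0.1, simulation gives:

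| Assumed split | Any one-class position | One-class and exact p < 0.05 |
|---|---|---|
| Equal thirds | 16–22% | 15–20% |
| 60/30/10 | 58–64% | 24–28% |
| 70/25/5 | 72–73% | 16–21% |

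Runs differ by about one percentage point, so the last column is roughly 15 to 29% overall. With no association (common selective share 0.3 to 0.5), any one-class position occurs in 0–3%, 12–29% and 38–53% respectively.

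**The case against.** The strongest reply is that little depends on this output. The secondary objectives are descriptive, with no performance requirement and no alpha. The code is offered as similar to what will be run, and the SAP introduction expects analyses beyond the plan, so an exact test or a Firth fit is already allowed. The text of 7.2.2 would itself be satisfied by a penalised or exact logistic regression. The same objective also compares HV intervals across positions by linear regression, which is untouched. All of this stands and keeps the point minor. It does not supply what is missing, because a descriptive aim still needs a finite estimate and interval, and being allowed to add a method later is not pre-specifying it.

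A second reply is that the fault in the p-value belongs to the Wald statistic and not to the likelihood. That is correct: TYPE3 in the existing call would recover an overall test. It would not give a usable odds ratio or limits.

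A reader might go further and infer that the plan would report a strong position effect as no effect, and would do so in most trials with a skewed split. The documents do not support either step. A standard error in the hundreds or thousands signals that the contrast is not estimable, and only someone relying on the p-value alone would read it as absence of effect. The 58 to 73% figures count every one-class position, including those of one or two leads, where the exact test often finds nothing either.

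**Conclusion.** The point holds as a conditional. If one septal position is all selective or all non-selective, the code in SAP 7.9.2 gives no usable estimate, interval or Wald p-value for contrasts with that position. All contrasts are lost only if it is the reference level. The data still carry the information: in the worked table the likelihood-ratio p is 0.006, the exact p is 0.02 and the Firth OR is 0.06.

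How likely this is cannot be taken from the documents. The figure of roughly 15 to 29% rests on the assumed shares 0.5/0.3/0.1 and the three assumed splits. With equal thirds and no association, a one-class position arises in 0 to 3% of draws. A one-class position is not in itself evidence of a strong effect. The consequence is confined to the interpretation of one descriptive secondary result, and the primary objective is unaffected.

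**What to change.** In SAP 7.9.2, with matching wording in 7.2.2:
- report odds ratios from Firth penalised logistic regression with profile-likelihood limits (PROC LOGISTIC with the FIRTH option), naming the reference position;
- take the overall test from the Fisher-Freeman-Halton exact test of the 3 × 2 table, or at minimum add TYPE3 to obtain the likelihood-ratio test;
- print the selective count and proportion with a Wilson interval for each position, a method the SAP already uses for the primary objective.

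The exact test is the better choice for the overall p-value, given how far the likelihood-ratio p falls below it when the one-class position has few leads. The protocol wording can stay.

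The cost is a few lines of SAP text and code, with no new data and no design change. The drawbacks are slight shrinkage of the odds ratios toward 1 when no position is sparse, and a slightly conservative exact test.

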7.2.3. Secondary Objective #2

This secondary objective is to assess changes in lead electrical measurements over time (HB PCT, R waves and impedance).

The lead electrical measurements from each visit will be summarized using descriptive statistics (mean, median, standard deviation, minimum, maximum, etc.) and graphical displays. Longitudinal analysis will

be conducted to estimate differences in electrical measurements from implant to subsequent follow-up visits.

7.2.4. Secondary Objective #3

This secondary objective is to assess changes in QRS duration over time.

The QRS durations from each visit will be summarized using descriptive statistics (mean, median, standard deviation, minimum, maximum, etc.) and graphical displays. Longitudinal analysis will be conducted to estimate differences in QRS duration from implant to subsequent follow-up visits.

7.2.5. Secondary Objective #4

This secondary objective is to estimate the correlation between implant characteristics and long-term lead electrical performance at 12 months post-implant.

A multivariable regression analysis will be conducted to assess if there is any correlation between implant characteristics, including lead location, HB PCT, and QRS duration at implant, and the 12-month HB PCT.

7.2.6. Secondary Objective #5

This secondary objective is to characterize the occurrence of any complications related to the procedure or the lead for His bundle pacing up to 12 months post-implant.

The types of complications related to the procedure or the lead for His bundle pacing will be summarized using frequencies and percentages. The probability of a subject being free of a complication related to the procedure or the lead for His bundle pacing through 12 months post-implant will be estimated using the Kaplan-Meier method. In addition, the relationship between implant characteristics, including lead position, HB PCT at implant, and QRS duration at implant, and the occurrence of complications related to the procedure or the lead for His bundle pacing will be assessed using a Cox proportional hazard regression model.

7.2.7. Ancillary Objective #1

This ancillary objective is to characterize the performance of existing delivery tools for the Medtronic SelectSecure™ MRI SureScan™ Model 3830 lead for HBP.

Responses to the Physician Questionnaire eCRF will be summarized using frequencies and percentages.

7.2.8. Ancillary Objective #2

This ancillary objective is to summarize implant procedure information.

The implant procedure information will be summarized using descriptive statistics (mean, median, standard deviation, minimum, maximum for continuous variables, and frequencies and percentages for categorical variables).

7.2.9. Ancillary Objective #3

This ancillary objective is to characterize the survival for subjects up to 12 months post-implant.

The causes of death will be summarized using frequencies and percentages. The probability of subject survival through 12 months post-implant will be estimated using the Kaplan-Meier method.

7.3. Center Pooling

The IMAGE-HBP study will be conducted at three sites. Given the small number of sites participating, there will be no analysis to examine the impact of site on study results.

7.4. Handling of Missing Data and Dropouts

If data is missing then there will be no imputation of the data. Instead, subjects with missing data will be excluded.

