7.9.3. Secondary Objective #2

This secondary objective is to assess changes in lead electrical measurements over time (HB PCT, R waves and impedance).

Analysis Dataset:

Analysis set #2 per section 7.1.3.

Analysis Method:

The lead electrical measurements from each visit will be summarized using descriptive statistics (number with measure available, mean, median, standard deviation, minimum, maximum) and graphical displays. Longitudinal analysis will be conducted to estimate differences in electrical measurements from implant to subsequent follow-up visits. The analysis will be performed in SAS using code similar to:

```
proc mixed data=analysisset2;
  class time;
  model pct = time;
  random int / subj=ptid corr=exch;
run;
```

Endpoint Definition:

The lead electrical measurements that will be evaluated include HB pacing capture threshold (PCT) (in Volts) at 0.5ms, impedance (in Ohms), and R-wave amplitude (in mV) measured at the final lead location during the implant procedure, and then at the 3-month, 6-month, and 12-month follow-up visits.

Additional Analysis:

A similar analysis will be performed using the HB PCT at a pulse width of 1.0ms, instead of a pulse width of 0.5ms.

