7.9.4. Secondary Objective #3

This secondary objective is to assess changes in QRS duration over time.

Analysis Dataset:

Analysis set #2 per section 7.1.3.

Analysis Method:

The QRS durations from each visit will be summarized using descriptive statistics (number with measure available, mean, median, standard deviation, minimum, maximum) and graphical displays. Longitudinal analysis will be conducted to estimate differences in QRS duration from implant to subsequent follow-up visits. The analysis will be performed in SAS using code similar to:

```
proc mixed data=analysisset2;
  class time;
  model inqrs = time;
  random int / subj=ptid corr=exch;
run;
```

Endpoint Definition:

Intrinsic QRS duration will be measured prior to the implant procedure, and then at the 3-month, 6-month, and 12-month follow-up visits.

Additional Analysis:

A similar analysis will be performed using the paced QRS duration instead of intrinsic QRS duration.

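### SAP 7.4 excludes subjects with missing data without limit, which conflicts with SAP 7.1.1, the mixed models in 7.9.3 and 7.9.4, and protocol 9.11; read literally, one missed visit would discard a subject's valid measurements for Objectives 2 and 3

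*SAP*

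**What the plan says.** Four parts of the SAP and two of the protocol bear on this.

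- **SAP 7.4**, the section on missing data and dropouts, allows no imputation and continues: "Instead, subjects with missing data will be excluded". The unit removed is the subject. No objective, measure or visit is named.
- **SAP 7.1.1** has a narrower rule: "If there is missing data that prevents the analysis of a pre-specified objective then those subjects will be excluded from that objective".
- **SAP 7.9.3** (lead measurements) and **7.9.4** (QRS duration) fit a mixed model with categorical time, for example "model inqrs = time", and a subject-level random intercept, "random int / subj=ptid corr=exch". Each visit is also summarised by "number with measure available, mean, median, standard deviation, minimum, maximum".
- **SAP 7.1.3** defines the set for these objectives by one condition: "Study subjects will be included in this analysis set if they have a successful implant". Completeness of follow-up is not required.
- **Protocol 9.11** states that data collected up to a subject's exit remain usable for analysis.
- **Protocol 9.8** treats a missed visit as a deviation and keeps later visits on their original schedule, so data after a missed visit are still collected.

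The time points are fixed. Lead measurements are "measured at the final lead location during the implant procedure, and then at the 3-month, 6-month, and 12-month follow-up visits". For QRS: "Intrinsic QRS duration will be measured prior to the implant procedure, and then at the 3-month, 6-month, and 12-month follow-up visits".

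**The concern.** Section 7.4 is where a programmer would look for the missing-data rule, and it gives the least favourable one. Taken at its word, a subject who misses month 6 also loses valid values from implant, month 3 and month 12. That wastes the main advantage of a random-intercept model, which uses every observed row. It also empties the available-number column of meaning, because within a measure that number could not vary between visits if only complete subjects remained.

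Two things are at stake. One is precision, in a study with at most a few dozen implanted subjects. The other is selection. Objective 2 asks how thresholds change, and SAP 7.9.6 lists lead dislodgement, loss of capture and high thresholds leading to action among the complications. A subject with such an event might lack later threshold values, and excluding that subject would remove the earlier values too. Two programmers following different sections of the same SAP could report different numbers of subjects and different changes.

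**Working it through.** **1. Figures that the plan gives.** The documents state no missing-visit rate and no precision for Objectives 2 and 3. The only related figures are the Wilson interval widths for the primary endpoint, which fix the planned numbers at an observed success of 0.9. With width = 2z/(1 + z²/n) × √(p(1−p)/n + z²/(4n²)) and z = 1.96:

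- SAP section 6, n = 50, p = 0.90: 0.1701, stated as 0.17.
- Protocol 13.1.3, n = 62, 56 successes: 0.1504, stated as 0.15.

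Both reproduce. Taking 90% success as an assumption, Analysis Set #2 has 0.9 × 50 = 45 subjects under the SAP (written from protocol version 2.0) and 0.9 × 62 ≈ 56 under the current protocol. Both are carried forward.

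**2. Subjects lost under the literal rule.** There are three follow-up visits (3, 6 and 12 months). Assume the implant value is always present and each follow-up value is missing independently with probability m. The complete fraction is (1 − m)³.

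| m (assumed) | (1 − m)³ | Lost | Remaining of 45 | Remaining of 56 |
|---|---|---|---|---|
| 5% | 0.857 | 14.3% | 38.6 | 48.0 |
| 10% | 0.729 | 27.1% | 32.8 | 40.8 |
| 15% | 0.614 | 38.6% | 27.6 | 34.4 |

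At m = 10% and 45 subjects, the model on all records would use 45 + 3 × 45 × 0.9 = 166.5 measurements. Complete subjects supply 4 × 32.8 = 131.2. About 35 valid measurements are discarded.

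**3. Precision.** This is an illustrative simulation with 45 subjects and 4,000 runs. Mean thresholds are 1.2, 1.3, 1.4 and 1.6 V at implant, 3, 6 and 12 months, so the true 12-month change is 0.40 V. The between-subject SD is 0.5 V and the residual SD 0.4 V. None of these values comes from the documents. The all-records arm is a random-intercept model with the variances taken as known. With values missing completely at random:

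| m | SE, all records | SE, complete subjects | Ratio |
|---|---|---|---|
| 5% | 0.086 | 0.091 | 1.06 |
| 10% | 0.087 | 0.099 | 1.14 |
| 20% | 0.091 | 0.119 | 1.31 |

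Both arms recover 0.40 V, so here the cost is precision only.

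**4. Bias.** The data model is the same, but subjects now drop out after month 3 or month 6. The log-odds of dropout are −2.5 + slope × (observed rise − 0.15 V).

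| Slope per V | All records | Complete subjects |
|---|---|---|
| 0 | 0.401 | 0.401 |
| 1 | 0.401 | 0.375 |
| 2 | 0.401 | 0.340 |
| 3 | 0.401 | 0.302 |
| −2 | 0.399 | 0.459 |

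The complete-subject estimate is too low if a rise makes dropout more likely, too high if it makes dropout less likely, and unbiased if there is no relation. The all-records model stays near 0.40 V because dropout here depends only on observed values and the model is correctly specified.

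**The case against.** The strongest reply is that the analysis as specified already keeps partial subjects. Section 7.1.1 excludes only where missing data prevents an objective's analysis, and one missed visit does not prevent a random-intercept model from running. Analysis Set #2 carries no completeness condition, the code has no completer filter, and the mixed procedure drops a missing row rather than a subject. A programmer would have to add a filter that the SAP does not contain. All of this stands. A reader might infer from 7.4 that the sponsor has settled on deleting subjects, or that 7.4 makes the mixed model impossible. The documents support neither: the model would also run on complete subjects, only with fewer data.

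The objection does not remove the conflict. Section 7.4 is the dedicated missing-data section, it states a rule in general terms, and it does not refer to 7.1.1.

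It is also fair to say that Objectives 2 and 3 are descriptive, with no performance requirement, and that the SAP expects further analyses beyond the plan. That limits the weight of the point.

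A last caution concerns intrinsic QRS. The documents do not say how absence of intrinsic rhythm at a visit is recorded, or whether it counts as missing. If the value cannot be measured because of the subject's conduction status, using all records saves that subject's other values but does not by itself resolve the selection.

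**Conclusion.** The point holds as an unreconciled conflict within the SAP, and between SAP 7.4 and protocol 9.11, in which the dedicated section gives the worse rule. If 7.4 were followed literally for Objectives 2 and 3, roughly 14% to 39% of subjects would be lost at 5% to 15% missingness per visit: 39, 33 or 28 would remain of about 45, or 48, 41 or 34 of about 56. These counts rest on 90% implant success and independent missingness. The 14% increase in standard error at 10% missingness also rests on the illustrative variances.

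It is tempting to conclude that threshold rise would be understated. The documents do not support a direction. Bias is nil under random missingness and can go either way otherwise (0.30 to 0.46 V against a true 0.40 V in the scenarios shown). With no rate or mechanism in the documents, its size is unknown.

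The primary endpoint is not affected: implant success is settled at the procedure, and missed follow-up visits do not bear on it. The correction is worth making before the analysis programs are run.

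**What to change.** In SAP 7.4, replace the exclusion sentence for these two objectives with wording such as:

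*For Secondary Objectives #2 and #3, a missing visit value is omitted and the subject contributes all other available visits to the mixed model. A subject is left out for a measure only if no value of that measure is available.*

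Align SAP 7.1.1 with this, so that a single missed visit is clearly not a reason for exclusion, and report the number contributing at each visit for each measure. An analysis restricted to complete subjects can be kept as a sensitivity analysis if wanted.

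The cost is one sentence in 7.4 and a matching clause in 7.1.1. No new data are needed. The main analysis needs no extra programming, since the code in 7.9.3 and 7.9.4 has no completeness filter.
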